1. SUMMARY OF THE STUDY

Background. Laparoscopic cholecystectomy is one of the most commonly performed surgical procedures worldwide. One of its most serious complications is injury to the main bile duct, with an incidence of less than 1%. There are different surgical strategies that attempt to reduce this complication, with indocyanine green fluorescence cholangiography being one of the most recent to appear. This technique is becoming a great tool during laparoscopic cholecystectomy. Despite the boom in the procedure, there is currently a wide disparity in the protocols for administration of indocyanine green during the procedure.

Objectives. The main objective of the study is to analyse whether there are differences between different types of doses and administration intervals of indocyanine green to obtain quality fluorescein cholangiography during laparoscopic cholecystectomy. In addition, factors influencing the results of the technique will be sought.

Material and Methods. Open multicentre randomised clinical trial with 4 intervention groups (two doses and two administration times). The expected duration of the study will be 12 months. The main variables to be studied will be the degree of identification critical anatomical structures during laparoscopic cholecystectomy. Patients will be analysed per protocol, without intermediate analyses.

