- 4- **Postoperative control visit.** This will take place 30 days after the surgical intervention through the General and Digestive System Surgery Outpatient Department.

There is no treatment period as it is considered a diagnostic method. This period shall include intraoperative time.

A computerised block randomisation will be performed through CDRe. Participants will be assigned to each of the 4 treatment groups by non-stratified 1:1:1:1 randomisation.

As it is an intervention without a control group, blinding will not be performed in the trial. The end-of-study criterion will be completion of the follow-up period at the end of the trial. 30 days from the last patient included in the study.

19. Effectiveness Assessment

The following efficacy parameters shall be used:

- Degree identification of biliary structures prior to dissection of the hepatocystic triangle (1=poor, 2=sufficient, 3=sufficient, 4=good, 5=excellent).
- Degree of identification of biliary structures after dissection of the hepatocystic triangle (1=poor, 2=sufficient, 3=sufficient, 4=good, 5=excellent).
- Degree to which FC was perceived as useful for surgery (0=not useful, 1=moderately useful, 2=very useful).
- Degree to which the fluorescence of the liver background (contrast between liver and ducts) was perceived as disturbed (0=absence of disturbance, 1=slightly disturbed, 2=disturbed visualisation, but cystic-choledochal junction was clearly visible before dissection, 3=disturbed visualisation and cystic-choledochal junction was only visible after dissection, 4=very disturbed: it was impossible to visualise the biliary structures correctly).

20. Security Assessment

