20.12. Report to researchers

The sponsor will submit safety information that could impact the safety of the patients enrolled in the trial to the investigators as early as possible. In addition, the investigator will be informed throughout the study of any safety issues, including protocol modifications due to safety concerns.

21. Statistics

For the calculation of the sample size we estimated an average annual number of laparoscopic cholecystectomies of 300 cases. Assuming a minimum recruitment rate of 50% in the study, a duration of 12 months and possible losses of patients, we estimate a sample size of 200 patients.

Since the main objective is to analyse whether there are differences between the doses and administration times of the 4 treatment groups in which categorical variables will be measured, the effect of the chosen sample size ($n=200$) on the statistical contrasts in this type of variables is $w=0.25$ with a power.95 and a significance error of the null hypothesis $\alpha=0.05$.

The procedure used to account for missing, unused and erroneous data will be the "*Pairwise Delection*" method. The confidence intervals of the statistics will be 95% and the contrasts will be performed at a significance level of 5%. All analyses will be performed with the free software R (version 4.1.2+, R Core Team, Vienna, <https://www.R-project.org/>) and the RStudio interface (version 1.4.1103+).

The study will have no planned intermediate analyses as no partial analysis of results is envisaged. Once all data have been collected, verified and validated, a statistical analysis of the data will be performed according to the specifications described in the protocol. If this analysis leads to the conclusion that further analysis is necessary, this will be reported in the final analysis of results. All treated and evaluable subjects shall be analysed. Different statistical tools will be used depending on the nature of the variables collected in the study, accompanying the results with their corresponding graphs.

Lilliefors-Kolmogorov-Smirnov and Shapiro-Wilks tests shall be performed to study the normality of the distribution of quantitative variables, and to their distribution they shall be represented by the mean (standard deviation) or the median (median deviation) and may be accompanied by their corresponding confidence intervals. The relationship between such variables shall be measured with Pearson's or Spearman's correlation coefficients.

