The distributions of the categorical variables will be studied by means of frequencies and percentages. To represent and measure the dependence between them, contingency tables will be used with Pearson's Chi-square test, Fisher's exact test, McNemar's test

or Cochran's Q. A category comparison study could also be done using odds ratios between categories of clinical interest. To study the influence that some categorical variables might have on quantitative variables, ANOVA tests could be performed.

Finally, all the statistical information obtained on the relevance of each variable in the study could be used to apply classification tools to the individuals in the study (decision trees, logistic regression, ROC curves).

22. Direct Access to Source Data/Documents

The Promoter will enter into appropriate arrangements to appoint a monitor to oversee this study and to liaise regularly with the site, including arranging site visits. The investigator agrees to allow the monitor direct access to all relevant documents and to give his/her time and that of his/her staff to the monitor to discuss the results and any issues of concern.

23. Quality Control and Quality Assurance

In order to ensure the quality of the data, the promoter:

- Provide quality instruction and training to the research staff prior to the start of the study. Training topics include, but are not limited to: Good Clinical Practice (GCP) certificates, Adverse Event (AE) reporting, study details and procedures, study documentation, informed consent, and patient recruitment.

- Conduct regular monitoring in accordance with the International Conference on Harmonisation (ICH) for Good Clinical Practice (GCP). Data will be assessed for compliance with the protocol and for accuracy in relation to the source documents. Monitors will verify that the clinical trial is conducted, that data are generated, documented and reported in compliance with the protocol, good clinical practice and any applicable local regulatory requirements.

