In these secondary objectives, we tried to analyse predictors of the quality of the fluorescence technique. To this end, we have found numerous factors in the literature that could influence cholangiography. We want to show whether there are differences between the factors listed below and the different working groups.

a) To analyse the influence of body mass index on FC outcomes during CL.

In this section, we could recode the qualitative variable BMI into the different BMI subgroups defined by the World Health Organisation or use normal weight/overweight as the cut-off point.

Clasificación	IMC (Kg/m ²
Normal	18.5 - 24.9
Sobrepeso	25 - 29.9
Obesidad grado I	30 - 34.9
Obesidad grado II	35 - 39.9
Obesidad grado III	Más de 40

We could also analyse it as a quantitative variable and see if there is a correlation between them.

b) To analyse the influence of the type of biliary pathology requiring surgery and previous liver disease on the results of FC during LC.

Analyse whether there are differences between "Previous liver disease (NO/SI). In the SI group, break down the variables: fatty liver disease, hepatitis, liver cirrhosis". And the main variables shown.

c) To analyse the influence of the type of surgery (elective/early/ delayed surgery) on the results of FC during LC.

To analyse whether there are differences between the variables "type of surgery" and "indication for surgery".

d) To analyse the influence of previous gallbladder or bile duct instrumentation on the results of FC during LC.

To analyse whether there are differences between the variables "previous biliary explorations", "previous biliary prostheses" and "previous gallbladder drainage". Both separately and united in a single variable.

e) To analyse the influence of different laparoscopic imaging systems on the results of FC during LC.

To analyse whether there are differences between the variable "image system" and the main target variables.

f) To analyse the rate of intraoperative complications related to CF during LC.

To analyse intraoperative complication rates in the series.

g) To analyse the rate of postoperative complications related to CF during LC.

To analyse the postoperative complication rate for the series overall and for each type of Clavien-Dindo classification (consecutive variable).

Also to analyse separately the rate of bile duct injury and the characteristics of bile duct injuries (consecutive variables).

Analyse in-hospital and 30-day mortality rates.

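### The predictor analyses in SAP section 3 a)–e) test factors at 5% each against unranked outcomes, with no lead outcome, multiplicity control or exploratory label

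*SAP*

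**What the plan says.** The Protocol summary announces the search: "In addition, factors influencing the results of the technique will be sought". SAP section 3 states the aim in similar terms: "In these secondary objectives, we tried to analyse predictors of the quality of the fluorescence technique".

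The outcomes come from SAP section 2: six yes/no identifications before dissection, the same six after dissection, and four graded scales. That makes 16 variables, none ranked above another.

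The items differ in how clearly they name their outcomes:

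- **b) liver disease** and **e) imaging system**: the instruction line names the main variables. For e) it is "To analyse whether there are differences between the variable 'image system' and the main target variables".
- **a) BMI** and **d) prior instrumentation**: the heading asks about influence on the fluorescence cholangiography results, but the instruction names no outcome. Item d) takes explorations, prostheses and drainage "Both separately and united in a single variable". Item a) leaves open WHO classes, a single cut-off or a continuous analysis.
- **c) type of surgery**: the heading asks about influence on the results, but the instruction compares type of surgery with indication for surgery.

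Protocol section 21 says "the contrasts will be performed at a significance level of 5" per cent and makes no exception for secondary objectives. Neither document ranks the secondary objectives, adjusts for the number of tests or describes them as exploratory.

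**The concern.** A search for predictors over many outcomes, each tested at 5%, produces some significant results by chance. Without a lead outcome or a stated status, the plan gives no basis for separating a real association from a chance one. It also does not prevent a single small p-value from being reported as an influence on fluorescence. The factors most exposed are those that readers may act on, such as the imaging platform, previous liver disease or earlier biliary drainage. The four versions of instrumentation and the open coding of BMI add further choices that could be made after the data are seen. This family is separate from the comparison of groups G1 to G4, so resolving multiplicity there would leave it unchanged.

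**Working it through.** **The plan's own figure.** Protocol section 21 states: "the effect of the chosen sample size ($n=200$) on the statistical contrasts in this type of variables is $w=0.25$ with a power.95". The noncentrality is n·w² = 200 × 0.25² = 12.5. At α = 0.05 with 1 df the power is 0.942, which agrees with the stated 0.95 to within a percentage point. (With the 3 df of a four-group yes/no table it is 0.856. That is a separate matter on which this point does not depend.) Neither document gives a familywise error rate to reproduce.

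**Inputs from the documents.** α = 0.05 per test; 6 + 6 + 4 = 16 main variables; two factors explicitly crossed with them.

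**Count under full crossing.** BMI once (1), liver disease yes/no (1), type of surgery (1), three instrumentation variables plus their combination (4) and imaging system (1) make 8 factor tests per outcome. This leaves out type of biliary pathology, which the heading of b) names but its instruction does not use; including it gives 9 × 16 = 144 tests. It also counts only one coding of BMI.

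**Assumptions, not in the documents.** No tested factor matters; outcome correlation between 0 and 0.8; factors independent or correlated 0.5.

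**Expected false positives** (m × 0.05, whatever the correlation): 32 tests give 1.6; 128 give 6.4; 144 give 7.2.

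**Chance of at least one, independent tests**, 1 − 0.95^m:

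- m = 16: 0.560
- m = 32: 0.806
- m = 128: 0.9986

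**Chance of at least one, correlated tests.** Two-sided z-tests were simulated with 40,000 replicates, the correlation matrix being the product of factor and outcome correlations:

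| Tests | Factor correlation | Outcome correlation 0 | 0.5 | 0.8 |
|---|---|---|---|---|
| 2 × 16 | 0 | 0.81 | 0.61 | 0.37 |
| 2 × 16 | 0.5 | 0.79 | 0.58 | 0.35 |
| 8 × 16 | 0 | 0.999 | 0.975 | 0.84 |
| 8 × 16 | 0.5 | 0.99 | 0.93 | 0.73 |

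Arithmetic check on the 0.61: one factor against 16 outcomes at correlation 0.5 gives 0.37, and two independent factors give 1 − 0.627² = 0.61.

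**Cross-check with actual tables.** Protocol section 21 says "contingency tables will be used with Pearson's Chi-square test, Fisher's exact test, McNemar's test" or Cochran's Q. A second simulation built contingency tables at n = 200, with assumed identification rates, chi-square tests (Fisher for sparse 2 × 2 tables) and 200 replicates per scenario. It gave 62–84% for the two explicit factors and 97–100% for 128 tests. Its eight factors were those named in the headings, without the combined instrumentation variable. It lies towards the upper end because a correlation set on an underlying scale weakens once variables are cut into categories, and 200 replicates leave a few points of noise.

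**A narrower set of outcomes.** If only the four graded scales were used (8 × 4 = 32 tests), the chance is 0.74 at outcome correlation 0.5 with independent factors.

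**The case against.** The strongest reply is that these are non-randomised secondary associations, described in tentative language: factors will be sought, they could influence the result, BMI could be recoded. Such analyses are often left unadjusted, and requiring formal adjustment is partly a matter of preference. That stands as an argument against compulsory adjustment. It does not remove the need to state the status of the analyses, because the same text speaks of predictors and influence and never says exploratory.

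The second reply concerns scope. A reader might infer that the SAP crosses every factor with all 16 variables. It does not say so. The crossing is written only for liver disease and imaging system, and the lead-in to section 3 even speaks of differences between the factors and the working groups. Full crossing is the natural reading of the headings, since the SAP defines no other fluorescence results, but it remains an inference. This reply stands.

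Third, a reader might infer a rule that one p-value below 0.05 among 16 makes a factor an influence. No such rule is written. What is missing is any rule at all.

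Fourth, the figures assume that nothing matters, while the SAP says the factors came from the literature. This is fair, but the risk does not depend on a complete null. If half of the 128 tests had true effects, the other 64 would give 1 − 0.95^64 = 96% if independent.

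Finally, a reader might infer that the results will be fed into decision trees or logistic regression. The Protocol says only that they could be, and the closing note of the SAP shows this is undecided.

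**Conclusion.** The concern holds in a limited form. SAP section 3 a) to e) seeks predictors at 5% per test against unranked outcomes, with no lead outcome, multiplicity control or exploratory label, and items a), c) and d) do not state which outcomes they use. If no tested factor matters, the two explicitly crossed factors carry about a 61% chance of at least one false-positive association (35–81%). Under full crossing the chance is about 73–99.9%. The ranges rest on assumed outcome correlations of 0 to 0.8 and factor correlations of 0 or 0.5.

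It would be too strong to say that false predictors are almost certain. That needs the full crossing, which is only implied, together with correlations away from the high end, and it treats every significant association as a declared predictor. Even so, the lowest figure for the two explicit factors, 35%, is seven times the nominal 5%. The remedy is inexpensive and worth making, but the defect does not touch the randomised comparison.

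**What to change.** In SAP section 3 a) to e):

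1. Name one lead outcome for all predictor analyses, for example the 1–5 degree of identification before dissection. This is the sponsor's choice: the Protocol summary points to degree of identification in general, and neither document ranks the pre-dissection grade above the post-dissection one.
2. Use one form of each factor. For d), make the combined instrumentation variable the single analysis and keep its three components descriptive. For a), fix one form of BMI.
3. State that a) to e) are hypothesis-generating and report the number of tests done. Give results on all other variables as estimates with 95% confidence intervals, without claims of prediction or influence.

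The label matters even with one lead outcome: eight unadjusted tests still give 1 − 0.95^8 = 34% if independent, and about 25% if the factors are correlated 0.5.

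The cost is wording only, with no new data or patients. The downside is weaker claims about the secondary factors.

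A Holm adjustment across factors is optional, needed only if the sponsor wants to claim a predictor. Its power cost depends on the test. At w = 0.25 and n = 200, moving from 0.05 to the strictest step, 0.05/8 = 0.00625:

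- 1 df (yes/no factor, yes/no outcome): 94% to 79%
- 4 df (yes/no factor, five-level outcome): 82% to 56%
- 8 df (three imaging systems, five-level outcome): 71% to 41%

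A test that uses the ordering of the grades would give different figures.

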20.4. Safety variables and parameters

The safety assessment of the drugs under study will be carried out by means of clinical examination (physical, analytical and/or radiological) and collecting serious adverse effects and those that may be directly related to the medication under study.

The key safety parameter will be the bile duct injury rate, which is currently at incidences of 0.3%-0.7%.

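### The SAP plans no by-arm safety summary: complications are specified for the whole series, and bile duct injury, mortality and late adverse reactions are listed with no arm named

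*SAP*

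**What the plan says.** SAP section 3 contains the safety analyses.

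- Item f), intraoperative complications: "To analyse intraoperative complication rates in the series".
- Item g), postoperative complications: "To analyse the postoperative complication rate for the series overall and for each type of Clavien-Dindo classification". It then asks for the rate and features of bile duct injuries, and for deaths in hospital and by day 30. Neither request says pooled or by arm.
- Item i), late adverse reactions and adverse events: rate and characteristics, from a separate spreadsheet, again with no arm named.

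Comparison across G1 to G4 is written in two places: the baseline table (SAP section 1) and the main-objective variables (SAP section 2). Neither list holds a safety outcome. Item h), on perceived usefulness, asks for results overall and also within each group, so the SAP says so when it wants a split.

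In the protocol, objectives 7 and 8 (section 8) concern rates of complications related to the technique. Section 20.4 states: "The key safety parameter will be the bile duct injury rate", and gives a current incidence of 0.3% to 0.7%. Section 12 confirms that all patients receive the product. Section 14 records intervention group, complications, bile duct injury and mortality for each patient. Section 21 names general contingency-table tests but no table of safety by arm.

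**The concern.** A complication rate pooled over four arms that all receive the dye has no concurrent comparator. It cannot separate what the dye or its schedule contributes from what the operation contributes. Randomisation does support contrasts between arms, between doses and between timings. Exposure differs between the dose arms: 0.05 mg/kg equals 2.5 mg only at 2.5 / 0.05 = 50 kg.

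If the SAP is carried out as written, a dose or timing could be favoured on visualisation with no safety outcome shown by arm beside it. A lone pooled interval would also look much tighter than what any one arm can exclude.

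**Working it through.** **The plan's own figure.** Protocol section 21 says "we estimate a sample size of 200 patients" and gives an effect size of w = 0.25 "with a power.95 and a significance error of the null hypothesis" at alpha 0.05. The noncentrality is 200 × 0.25² = 12.5. With 1 degree of freedom the power is 0.942, close to the stated 0.95. With 3 degrees of freedom (four arms by yes/no) it is 0.856. Either way, the figure is tied to the main objective. The documents give no power or precision for a safety outcome.

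**Group sizes.** Protocol section 18: "Participants will be assigned to each of the 4 treatment groups by non-stratified 1:1:1:1 randomisation". If all 200 are enrolled, that is 200 / 4 = 50 per arm and 100 per dose or timing level.

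**What zero events would exclude.** The exact two-sided 95% upper limit for 0/n is 1 − 0.025^(1/n).

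- n = 50 (one arm): 7.1%
- n = 100 (one factor level): 3.6%
- n = 200 (pooled): 1.8%

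The pooled limit is about a quarter of the per-arm limit (1.8 / 7.1 = 0.25).

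Section 21's minimum recruitment of 50% of 300 cases gives 150 patients. The same formula then gives 9.5% (n = 37, since 150 / 4 = 37.5), 4.8% (n = 75) and 2.4% (n = 150).

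**Bile duct injury.** Expected events in the trial are 200 × 0.003 = 0.6 to 200 × 0.007 = 1.4. Per arm they are 50 × 0.003 = 0.15 to 50 × 0.007 = 0.35. Against an arm with no injuries, Fisher's exact test at 5% needs 6 events: for 50 v 50, p = 2 × C(50,6) / C(100,6) = 0.027, while 5 v 0 gives 0.056. Six are also needed at 100 v 100. Exact power for 0.7% v 1.4% is 0.01% at 50 v 50 and 0.15% at 100 v 100. For 80% power, 3,328 per group would be needed.

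**Overall complications.** The documents give no baseline rate, so 5% to 20% is assumed. Power to detect a doubling, two-sided 5%:

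| Assumed baseline | 50 v 50 (Fisher) | 100 v 100 (Fisher) | Four arms, one factor doubles the rate (chi-square, 3 df) |
|---|---|---|---|
| 5% | 6% | 19% | 18% |
| 10% | 19% | 44% | 35% |
| 15% | 35% | 67% | 55% |
| 20% | 52% | 84% | 74% |

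The dose and timing margins therefore carry some information on complications. Single-arm contrasts carry less, and bile duct injury carries essentially none.

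**The case against.** The best defence is that the plan matches its objectives. Objectives 7 and 8 ask for rates, not differences, and the trial's hypothesis concerns visualisation. For bile duct injury, the 0.3% to 0.7% in protocol section 20.4 is an external reference. The lead-in to SAP section 3 mentions looking for differences involving the working groups. Protocol section 21 provides chi-square and Fisher tests, allows odds ratios between categories of clinical interest, and lets further analyses be reported. Nothing forbids a by-arm table.

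Part of this stands. A by-arm table is not excluded, and overall rates do answer objectives 7 and 8 as worded. But the lead-in is about predictors of fluorescence quality, and f) and g) then name the series. The section 21 tests are a general toolkit that assigns no safety outcome to an arm comparison. The external reference does not help to choose between arms, and even 0/200 leaves an upper limit of 1.8%, above 0.7%.

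A reader might infer two stronger things that the documents do not support. The first is that bile duct injury and mortality are explicitly restricted to a pooled analysis; the SAP is silent there. The second is that pooling is why the trial cannot say whether dose or timing affects safety. For bile duct injury the reason is sample size. For complications the data exist by arm, so a comparison remains possible and is merely unplanned.

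**Conclusion.** The point holds as a gap in specification. No by-arm safety summary is prespecified. Pooling is explicit for intraoperative and postoperative complications, while for bile duct injury, mortality and late adverse reactions no arm is named.

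The gain from closing the gap is moderate for overall complications: roughly 19% to 84% power for a doubling across a dose or timing margin, if baseline rates lie between 5% and 20% and all 200 patients are enrolled and evaluable. For bile duct injury the gain is only honest display of counts and intervals. The documents give no mortality rate; if deaths are as rare as bile duct injuries, the same applies. This is a cheap improvement worth making, and it does not threaten the primary analysis.

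**What to change.** Amend SAP items f), g) and i) as follows.

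1. Keep the overall rates as a descriptive line.
2. Add counts and rates with exact 95% confidence intervals by randomised group.
3. For overall intraoperative and overall postoperative complications, add risk differences with 95% confidence intervals by dose and by timing (about 100 v 100 if all 200 are enrolled).
4. For bile duct injury and mortality, give by-arm counts and exact intervals only.
5. State that the trial is not powered for safety differences, citing the 0.6 to 1.4 expected injuries and the 7.1% limit for 0/50, and that no claim of equal safety between arms will be made.

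The cost is SAP wording and a few table columns. Treatment group is already recorded for each patient, so no new data are needed. The downside is that wide by-arm intervals must be shown.
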